4.1.5 Blinding and procedures for unblinding

4.1.5.1 Blinding

In this open-label trial, treatment allocation will not be concealed throughout the trial. The trial will be handled in an open fashion by the Sponsor during the conduct, data cleaning and preparation for analysis.

4.1.5.2 Unblinding and breaking the code

Not applicable.

4.1.6 Packaging, labelling, and re-supply

The investigational products will be provided by BI or a designated CRO. They will be packaged and labelled in accordance with the principles of Good Manufacturing Practice (GMP). Re-supply to the sites will be managed via an IRT system, which will also monitor expiry dates of supplies available at the sites.

For details of packaging and the description of the label, refer to the ISF.

4.1.7 Storage conditions

Drug supplies will be kept in their original packaging and in a secure limited access storage area according to the recommended storage conditions on the medication label for anastrozole, letrozole and fulvestrant. For recommended storage conditions regarding abemaciclib and xentuzumab, please refer to the medication label. A temperature log must be maintained for documentation.

Abemaciclib will be supplied as capsules or tablets for oral administration. The capsules and tablets should be stored at room temperature according to the range provided on the product label and not opened, crushed, or dissolved. Investigators should instruct patients to store the capsules and tablets in the original package and in a location inaccessible to children. Clinical study materials will be labelled according to country regulatory requirements.

Xentuzumab is supplied as a liquid formulation at a concentration of 10 mg/mL in 20 mL single use vials, which contain 200 mg of xentuzumab per vial. All vials containing xentuzumab must be kept refrigerated according to the temperature range provided on the product label prior to dosage preparation.

The vials should not be frozen or shaken and should be kept in the outer carton in order to protect from light. They should not be used beyond the expiration date.

If the storage conditions are found to be outside the specified range, the local clinical monitor (as provided in the list of contacts) must be contacted immediately and product quarantined.

4.1.8 Drug accountability

The Investigator and/or Pharmacist and/or investigational drug storage manager will receive the investigational drugs delivered by the sponsor when the following requirements are fulfilled:

- * Approval of the trial protocol by the IRB / ethics committee and HA approval,
- * Availability of a signed and dated clinical trial contract between the sponsor and the head of the investigational site,

- * Approval/notification of the regulatory authority, e.g. competent authority,
- * Availability of the curriculum vitae of the principal Investigator,
- * Availability of a signed and dated clinical trial protocol,
- * Availability of the proof of a medical license for the principal Investigator,
- * Availability of Form 1572 (USA specific requirement)

The Investigator and/or Pharmacist and/or investigational drug storage manager must maintain records of the product's delivery to the trial site, the inventory at the site, the use by each patient, and the return to the sponsor or warehouse / drug distribution centre or alternative disposal of unused products. If applicable, the sponsor or warehouse / drug distribution centre will maintain records of the disposal.

These records will include dates, quantities, batch / serial numbers, expiry ('use- by') dates, and the unique code numbers assigned to the investigational product and trial patients. The Investigator / Pharmacist / investigational drug storage manager will maintain records that document adequately that the patients were provided the doses specified by the CTP and reconcile all investigational products received from the sponsor. At the time of return to the sponsor and/or appointed CRO, the Investigator / Pharmacist / investigational drug storage manager must verify that all unused or partially used drug supplies have been returned by the clinical trial patient and that no remaining supplies are in the Investigator's possession.

4.2 OTHER TREATMENTS, EMERGENCY PROCEDURES, RESTRICTIONS

4.2.1 Other treatments and emergency procedures

There are no special emergency procedures to be followed.

Symptomatic treatments of tumour-associated symptoms are allowed. Concomitant medications or therapy to provide adequate supportive care may be given as clinically necessary.

After study enrolment, palliative radiotherapy may be given for analgesic purposes, lytic lesions at risk of fracture or for other reasons (e.g. bronchial obstruction, skin lesions), provided that the total dose delivered is in a palliative range to non-target lesion according to institutional standards. Information on palliative radiotherapy will be captured in eCRF. It is at the investigator's discretion to withhold the study treatment during palliative radiotherapy. The investigators should assess the signs/symptoms carefully to exclude the progressive disease prior to the administration of the palliative radiotherapy.

The acute use of bisphosphonates and denosumab for symptomatic treatment of bone metastases is permitted during the study, but chronic use for the prevention of bone metastases is prohibited. Bisphosphonate therapy for the treatment of osteoporosis, at the doses indicated under prescribing information, is permitted during the study. If bisphosphonate therapy is initiated after enrolment, the reason for its use must be clearly documented in the eCRF.

All medications (other than study drug), including anaesthetic agents, vitamins, homeopathic/herbal remedies, nutritional supplements, and significant non-drug therapies (including physical therapy and blood transfusions) starting or changing after the patient signed informed consent must be listed on the concomitant medication page of eCRF including trade name, start and end dates, indication for use etc. as specified in the [Flow Chart](#).

If patients receive parenteral nutrition during the trial, the components need not be specified in detail. It should just be indicated as “parenteral nutrition”. If a patient requires anaesthesia, it will be sufficient to indicate “anaesthesia” without specifying details.

In case of major surgery (as judged by the investigator), it is recommended to stop treatment with xentuzumab and/or abemaciclib around one week prior to the surgery, and to restart treatment after complete wound healing. If the patient can't recover within 28 days since stopping study medication, patient should be removed from the study. Exception to this in patients who derive obvious clinical benefit according to the investigator's judgement could be agreed upon discussion with the Sponsor's Clinical Monitor.

4.2.2 Restrictions

4.2.2.1 Restrictions regarding concomitant treatment

With the exceptions listed in the sections below, no other chemotherapy, experimental medications, other anticancer therapy, including but not limited to immunotherapy, hormonal cancer therapy, radiation, experimental medications, or surgery for cancer will be permitted while patients are on study treatment. Use of megestrol acetate as an appetite stimulant is not permitted.

Abemaciclib is extensively metabolized through oxidation by CYP3A. In clinical drug interaction studies, coadministration of clarithromycin, a strong CYP3A inhibitor, increased exposure (AUC) to abemaciclib by 3.4 fold (Study JPBE) and coadministration of rifampin, a strong CYP3A inducer, decreased exposure to abemaciclib by 95% (Study JPBF). Therefore, grapefruit juice should be avoided and inducers and strong inhibitors of CYP3A should be substituted or avoided whenever possible (See [Appendix 10.1](#)).

During PK assessments of abemaciclib, the concomitant use of inhibitors or inducers of CYP3A4 should be avoided whenever possible, i.e. during Run-In, course 1 and course 2 of cohort E and during course 1 and 2 of expansion cohorts D1, D2 and F.

Apart from those assessments, patients are recommended to avoid concomitant use of strong CYP3A inhibitors and use caution with coadministered moderate or weak CYP3A inhibitors. Patients who continue to take strong CYP3A inhibitors should reduce the abemaciclib dose. In patients who are taking the starting dose of 150 mg twice daily, reduce the abemaciclib dose to 100 mg twice daily or, specifically in the case of ketoconazole, the abemaciclib dose should be reduced to 50 mg twice daily. In patients who have had a dose reduction to 100 mg twice daily due to adverse reactions, further reduce the abemaciclib dose to 50 mg twice daily. If a patient taking abemaciclib discontinues a strong CYP3A inhibitor, increase the abemaciclib

dose (after 3-5 half-lives of the inhibitor) to the dose that was used before starting the strong inhibitor. Please refer to current SmPC of Verzenio (abemaciclib).

In case it is unavoidable to treat a patient with a comedication that is a moderate to potent inducer or inhibitor of CYP3A4 dose adaptation of abemaciclib should be done as described above and according to the SmPC of Verzenio (abemaciclib). Furthermore, the patient should be closely monitored and precautions should be taken as described in the SmPC of Verzenio (abemaciclib).

Abemaciclib can be coadministered with drugs which are substrates of CYP enzymes.

Abemaciclib and/or its major metabolites inhibit the efflux transporters P-glycoprotein and breast cancer resistance protein and renal transporters organic cation transporter 2, multidrug and toxin extrusion protein 1 (MATE1), and MATE2-K at clinically relevant concentrations. Therefore, substrates of these transporters such as metformin and those with a narrow therapeutic index such as digoxin, dofetilide, or dabigatran should be substituted or avoided if possible.

Restrictions regarding concomitant treatment with fulvestrant, letrozole or anastrozole: please refer to the most up to date labelling information of each product, as appropriate (i.e. depending on the treatment cohort).

4.2.2.2 Restrictions on diet and life style

Patients have to show up in fasting condition at the site when blood draw for safety lab is required.

Grapefruit and/or Seville orange juices must be avoided during treatment with abemaciclib.

4.2.2.3 Restrictions regarding men and women of childbearing potential

Women of childbearing potential must use the contraception methods described in the patient information per ICH M3 (R2) that result in a low failure rate of less than 1% per year when used consistently and correctly. A list of contraception methods meeting these criteria is provided in the patient information, and must be used from the screening period until 3 weeks following the last dose of abemaciclib and at least 6 months after the last dose of xentuzumab.

Men should not father a child during treatment with xentuzumab and for at least 70 days after the last dose of xentuzumab.

4.2.2.4 Supportive Care

Patients should receive full supportive care to maximize quality of life. Patients will receive supportive care based on the judgment of the treating physician. If it is unclear whether a therapy should be regarded as supportive care, the investigator should consult the BI clinical monitor.

Use of any supportive care therapy should be reported on the electronic case report form (eCRF).

4.2.2.5 Growth Factor Therapy

Growth factors may be administered in accordance with American Society of Clinical Oncology guidelines (Smith et al. 2006; Rizzo et al. 2008).

4.2.2.6 Therapy for Diarrhoea

At enrolment, patients should receive instructions on the management of diarrhoea. In the event of diarrhoea, supportive measures should be initiated as early as possible. These include the following:

- * At the first sign of loose stools, the patient should initiate anti-diarrheal therapy, if not already receiving such therapy (for example, loperamide), and notify the investigator/site for further instructions and appropriate follow-up.
- * Patients should also be encouraged to drink fluids (for example, 8 to 10 glasses of clear liquids per day).
- * Site personnel should assess response within 24 hours.
- * If diarrhoea does not resolve with anti-diarrheal therapy within 24 hours to either baseline or Grade 1, study drug should be suspended until diarrhoea is resolved to baseline or Grade 1.
- * When study drug recommences, dosing should be adjusted, refer to the dose adjustment guidelines in [Section 4.1.4.2](#).

In cases of significant diarrhoea, Grade 2 through 4 which has not responded to interventions as outlined above, if the investigators are considering the addition of steroids to treat potential colitis, the sponsor strongly recommends an endoscopic procedure to document colitis prior to initiating steroids.

In severe cases of diarrhoea, the measuring of neutrophil counts and body temperature and proactive management of diarrhoea with antidiarrheal agents should be considered.

If diarrhoea is severe (requiring IV rehydration) and/or associated with fever or severe neutropenia, broad-spectrum antibiotics such as fluoroquinolones must be prescribed.

Patients with severe diarrhoea or any grade of diarrhoea associated with severe nausea or vomiting should be carefully monitored and given intravenous fluid (IV hydration) and electrolyte replacement.

4.2.2.7 Ovarian suppression with gonadotropin-releasing hormone agonists

Patients who are postmenopausal due to ovarian suppression should continue GnRH agonist therapy during study treatment.

4.3 TREATMENT COMPLIANCE

The study medications will be given in accordance with the protocol and the instructions of a site investigator. The investigator should instruct the patient to take the study drugs exactly as prescribed to promote compliance.

A patient will be considered noncompliant if he or she is judged by the investigator to have intentionally or repeatedly taken more than 125% the prescribed amount of abemaciclib or less than 75%. Abemaciclib dose suspensions or delays related to toxicity may occur and will not result in a patient being considered as noncompliant. Same rules apply to background hormonal therapy.

Patients are requested to bring all remaining trial medication including empty package material with them when attending visits.

Based on counts, treatment compliance will be calculated as the number of doses taken, divided by the number of doses which should have been taken according to the scheduled period, multiplied by 100. Compliance will be verified by the on-site monitor authorised by the sponsor.

$$\text{Treatment compliance (\%)} = \frac{\text{Number of doses actually taken} \times 100}{\text{Number of doses which should have been taken}}$$

If the number of doses taken is not between 75-125%, site staff will explain the patient the importance of treatment compliance.

The investigator and/or the sponsor can withdraw a patient from the study in the event of serious and persistent non-compliance which jeopardizes the patient's safety or render study results.

Xentuzumab will be administered as a single infusion under supervision of the investigator or dedicated study personnel. In the event that the full dose of xentuzumab is not administered to the patient, it must be documented and explained.

A maximum of three consecutive xentuzumab infusions may be skipped for the recovery from AEs. Missing xentuzumab treatment for any other reasons is considered non-compliant.

Patient diary for cohort E

For the purpose of PK characterisation of abemaciclib, patients of cohort E will be dispensed a patient diary two times during the conduct of the study: at run-in visit 1 and again at Cycle 1 visit 4. These patient diaries will collect information about daily intake of abemaciclib and potential vomiting events. The first patient diary will collect information during the 3 days prior to Run-In Visit 3. The second patient diary will collect information of the 3 days before Cycle 2 Visit 1. Site staff will be required to transfer the data from the patient diary into the corresponding eCRF fields.

4.4 MANAGEMENT OF EXPECTED ADVERSE EVENTS.

4.4.1 Increased Serum Creatinine

Abemaciclib has been shown to increase serum creatinine due to inhibition of renal tubular secretion of creatinine without affecting glomerular filtration rate (GFR [as measured by ioxhexol clearance]). In clinical studies, increases in serum creatinine occurred within the first month of abemaciclib dosing (remainder elevated but stable through the treatment period), were reversible upon treatment discontinuation, and were not accompanied by changes in markers of renal function such as blood urea nitrogen, cystatin C, or calculated GFR based on cystatin C.

Dose adjustment (omission, reduction, or discontinuation) should not solely be based on interpretation of serum creatinine values because these may not reflect renal function. If deterioration of renal function is suspected per the investigator's clinical assessment, dose alteration should follow the protocol guidance for non-hematological toxicities ([Section 4.1.4.2](#)).

4.4.2 Management and grading of infusion reactions

The xentuzumab infusion should always be administered under close supervision of a medically qualified staff member with immediate availability of appropriate resuscitation facilities.

Infusion reactions may occur during infusion with xentuzumab and include pyrexia, chills, rigors, dyspnoea, urticaria, bronchospasm, hypotension and hypertension. **A one hour observation period is recommended following each infusion.** If there is no infusion reaction during the first treatment course, the observation period following xentuzumab infusion may be adjusted at the discretion of the investigators. Mild to moderate infusion reactions may be managed with a slower infusion rate and prophylactic antihistamines for subsequent dosing. Severe reactions require immediate and permanent discontinuation of infusion. The hypersensitivity reactions will be graded according to the National Cancer Institute (NCI) Common Terminology Criteria for Adverse Events (CTCAE) version 4.03 ([R10-4848](#)).

The infusion duration may be extended to over one hour and up to a maximum of three hours.

The infusion reactions should be treated symptomatically as judged clinically relevant by the investigator. For symptomatic treatment of infusion reactions: hydrocortisone, antihistamines such as chlorphenamine accompanied by an antipyretic/analgesic and/or a bronchodilator is recommended.

Infusion reactions will not be reported on the standard AE page but will be reported on a separate page specifically for infusion reactions in the CRF.

Table 4.4.2: 1 Infusion reaction management

Infusion Reaction Grade	Management
CTCAE Grade 1 or 2	In the event of a CTCAE grade 1 infusion reaction, the infusion rate should be reduced by 50%. A Grade 2 infusion reaction may require symptomatic treatment, as described above (with infusion interruption). Once the event has resolved, the infusion may be restarted at the reduced rate.
CTCAE Grade 3	For patients experiencing a CTCAE grade 3 infusion reaction, infusion should be interrupted immediately and patients should receive aggressive symptomatic treatment, as described above. Only after all the symptoms have disappeared, the infusion may be re-started if it is within 3 hours since the infusion start. The infusion rate should be reduced by half after re-start
CTCAE Grade 4	Patients experiencing CTCAE grade 4 such as anaphylaxis during an infusion should have infusion immediately stopped and receive appropriate treatment, as described above, including use of resuscitation medications If needed. Such patients should NOT receive any further xentuzumab treatment.

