No relevant hyperglycaemia has been observed so far. Xentuzumab was well tolerated, with no relevant side effects reported. The type and pattern of adverse events (AEs) observed to date have generally been of mild to moderate intensity (CTCAE Grades 1 or 2) or consistent with the safety profile of combination backbone treatment or consistent with the underlying neoplastic conditions of patients enrolled on the study. The most frequently reported AEs for xentuzumab monotherapy were fatigue, decreased appetite, nausea, diarrhoea, and vomiting. Infusion-related reaction (IRR) is a listed side effect of xentuzumab treatment.

Promising early efficacy signals in the dose escalation part of the 2 phase I studies have been observed with two confirmed antitumour responses (Partial Responses) according to RECIST criteria in a patient with nasopharyngeal cancer and a patient with a peripheral primitive neuroectodermal tumour (PPNET) or Ewing sarcoma. Moreover, twelve confirmed disease stabilizations (SD) have been observed in heavily pre-treated patients suffering from advanced or metastatic solid tumours. In the expansion cohorts at R2PD, no further objective responses have been observed.

At a planned interim analysis of the randomized phase II part, based on the recommendation of data monitoring committee, recruitment of phase II part was stopped and xentuzumab treatment was discontinued. According to latest analysis, in the overall population, PFS did not improve with the addition of xentuzumab to everolimus plus exemestane. Nevertheless, a favorable signal was observed in the pre-specified subgroup of patients without visceral metastasis (report [c22665932-01](#)).

In the aforementioned ongoing trial in HR+ metastatic breast cancer, the safety profile of xentuzumab in combination with everolimus and exemestane is considered favourable and as expected, since the observed safety profile of this triple combination is consistent with previously reported data for the combination doublet everolimus and exemestane (Bolero-2 trial) (Baselga et al. 2011: [R12-5635](#)). The same applies for the combination with enzalutamide in CRPC, where the safety profile of this doublet is consistent with previously reported data for enzalutamide (Affirm and Prevail trials) ([R13-1229](#), [R15-1307](#)).

Abemaciclib

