4.1.4.1 Initial study drug assignment and administration

General information that applies in this study regardless of IRT is described in below sections of individual study drug. The medication kit as well as the treatment will be assigned with the support from IRT.

Before entering patients at the next dose level of the dose finding cohorts, it will be ensured that all patients at the current ongoing dose level have completed at least one course of treatment.

Xentuzumab

Patients will start treatment with their assigned dose tier (see [Section 4.1.2](#)) or RP2D of xentuzumab from course 1 day 1. Xentuzumab will be administered at the investigator site intravenously over one hour with a constant infusion rate on the treatment day as specified in the [Flow Chart](#). If scheduled infusion of xentuzumab is not performed within the time window, this treatment will be skipped and will not be made up. Subsequent visits should follow the original visit date schedule. Mannitol is used in the formulation of xentuzumab, so infusion duration of less than one hour must be avoided. The infusion time may be extended to over one hour and up to a maximum of three hours in cases of CTCAE grade ≥ 2 infusion reactions. In case of a delay or an interruption of infusion, the reason and the exact time of deviation must be recorded in the specific eCRF. The accuracy of this information is crucial for the proper evaluation and appraisal of the pharmacokinetics – in the relevant cohorts – and other data.

Detailed information of dispensation, preparation, and handling of xentuzumab will be described in ISF.

Abemaciclib

Abemaciclib will be taken orally every 12 (± 2) hours on days 1 through 28 of a 28-day cycle for a total of 56 doses per cycle. During all cycles, abemaciclib should be taken at approximately the same times each day. If a patient misses or vomits a dose, that dose should be omitted.

No more than 56 doses of abemaciclib should be dispensed for each 28-day cycle.

Abemaciclib dose omissions will be evaluated on a case by case basis and patients may be replaced if dose omissions occur within MTD period of a dose finding cohort or if the number of dose omissions makes the patient non evaluable regardless of the cohort.

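### Section 4.4.2 gives incompatible instructions on whether an infusion stopped for a Grade 3 reaction may be resumed

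*Protocol*

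**What the plan says.** Protocol Section 4.4.2 grades infusion reactions by CTCAE version 4.03. Its narrative uses two categories. For the lower one: "Mild to moderate infusion reactions may be managed with a slower infusion rate and prophylactic antihistamines for subsequent dosing". For the upper one: "Severe reactions require immediate and permanent discontinuation of infusion". The narrative also lets the infusion be lengthened beyond one hour, up to three hours, with no grade condition.

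Table 4.4.2:1, in the same section, works by grade:

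- **Grades 1 or 2** (one row): the rate is halved at Grade 1. Grade 2 may need interruption and symptomatic treatment, with a restart at the reduced rate.
- **Grade 3**: "For patients experiencing a CTCAE grade 3 infusion reaction, infusion should be interrupted immediately", with symptomatic treatment. Then: "Only after all the symptoms have disappeared, the infusion may be re-started if it is within 3 hours since the infusion start". And: "The infusion rate should be reduced by half after re-start".
- **Grade 4**: the infusion stops. "Such patients should NOT receive any further xentuzumab treatment".

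Other relevant places:

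- Section 1.2 says that the adverse events seen so far "have generally been of mild to moderate intensity (CTCAE Grades 1 or 2"). Section 2.3 repeats this.
- Section 4.4.3 labels neutropenia of Grade 3 or above as severe.
- Section 2.3 says that infusion reactions in this trial are graded and treated by usual care or local guidelines.
- Section 4.1.4.1: "The infusion time may be extended to over one hour and up to a maximum of three hours in cases of CTCAE grade" 2 or higher. Section 4.1.1 says the same.
- SAP Table 6.2:1, category C2, covers xentuzumab not given according to the protocol and is judged by individual review. Category C3 flags infusions shorter than 50 or longer than 200 minutes, with duration calculated allowing for interruptions.

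**The concern.** The narrative and the Grade 3 row answer one bedside question differently: once a Grade 3 reaction has settled, may this infusion go on? A site that relies on the narrative would end the infusion. A site that relies on the table could resume it. Infusion-related reaction is a listed side effect of xentuzumab, and the question arises just when staff are deciding whether to re-expose a patient who has reacted.

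The reporting consequence is narrower. C2 turns on whether xentuzumab was given according to the protocol. A resumed Grade 3 infusion complies with the table and departs from the narrative, so that question has no single answer. Two reviewers could code the same event differently, and each could cite the protocol.

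Both statements stand in the revision dated 4 March 2022, so this is not a difference between current and superseded text.

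**Working it through.** The main point is a consistency check on wording. The only arithmetic is for the size of the problem and for the infusion-time limit.

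**1. Narrative and table side by side**

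| Grade | Narrative of 4.4.2 | Table 4.4.2:1 | Agree? |
|---|---|---|---|
| 1–2 | Slower rate, antihistamine cover for later doses | Reduced rate; at Grade 2, possible interruption and restart | Yes |
| 3 | Halt at once, permanently (if *severe* includes Grade 3) | Halt at once; same infusion may resume at half rate | No, on resumption |
| 4 | Halt at once, permanently | Halt at once; no further xentuzumab | Yes |

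**2. Does *severe* include Grade 3?** Section 4.4.2 does not say. Three things point the same way:

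- Sections 1.2 and 2.3 gloss mild to moderate as Grades 1 or 2, which leaves Grade 3 as the first grade above it.
- Section 4.4.3, the next subsection, starts *severe* at Grade 3.
- The table puts Grades 1 and 2 in one row and separates Grade 3, matching the narrative's split.

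**3. Can another reading remove the conflict?**

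- *Severe means Grade 4 only.* This would remove it. But 4.4.2 does not say so, Grade 3 would then sit in neither narrative category, and the usage in step 2 is against it.
- *Permanent refers only to that day's infusion.* This does not help, because the infusion the Grade 3 row allows to resume is that same infusion.
- *Section 2.3 governs.* Deferring to local practice adds a third source and does not choose between the other two.

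**4. Frequency.** Section 1.2 gives about 494 patients treated in the xentuzumab programme at 18 January 2019. Section 2.3 gives 3 serious infusion reactions, 1 of them Grade 3 or higher.

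- Serious reactions: 3/494 = 0.6%.
- Serious and Grade 3 or higher: 1/494 = 0.2%.

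This assumes that both counts share a cut-off and that all 494 received xentuzumab. Non-serious Grade 3 reactions are not reported, so 0.2% may understate Grade 3 events.

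**5. The three-hour maximum (secondary).** Take the standard 60-minute infusion at constant rate, stopped at minute t and resumed at minute s at half rate.

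- Time needed for the rest: 2 × (60 − t).
- Running time, pauses excluded: t + 2 × (60 − t) = 120 − t, so never above 120 minutes.
- Elapsed time, pauses included: s + 2 × (60 − t).

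With t = 15 and a restart just before s = 180, the remainder takes 90 minutes. Running time is 105 minutes and elapsed time is about 270 minutes (4.5 hours). With t = 30 and s = 175, the remainder takes 60 minutes; running time is 90 minutes and elapsed time 235 minutes.

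Both examples are within three hours on running time and beyond it on elapsed time. They also fall on different sides of the 200-minute threshold in C3 (105 against 270; 90 against 235). The protocol does not say which count applies.

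**The case against.** The strongest case against is that the conflict is narrow. The Grade 3 row says the infusion *may* be resumed, and only after all symptoms have gone. Both texts require an immediate halt at Grade 3, and they agree at Grades 1–2 and Grade 4. A site that did not resume would breach neither text. Section 4.4.2 never gives *severe* a grade, so the mapping comes from other sections. All of this is correct. It confines the problem to one optional step, but it does not remove it: one sentence rules out what another allows.

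A reader might infer more than the documents support in three ways:

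- **That the extension rules contradict each other.** Sections 4.1.1 and 4.1.4.1 mention a longer infusion for Grade 2 or higher, while the table halves the rate at Grade 1, which lengthens a one-hour infusion. But neither section restricts extension to Grade 2 or higher, and 4.4.2 allows it with no grade condition. A single halving gives at most two hours. This is a wording mismatch.
- **That a late restart cannot finish within three hours.** This holds only if pauses count as infusion time, which the protocol does not say. The SAP's allowance for interruptions in C3 can be read as excluding them.
- **That deviations cannot be judged at all.** C3 gives a duration rule that does not depend on grade, and C2 provides for medical review. The gap is whether a Grade 3 restart is itself a deviation.

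Exposure under this revision is also limited. The sponsor recommended stopping xentuzumab on 19 October 2021, and supply ends by May 2023 (Section 3.3.4.2). The point is not moot, because continuation was left to individual investigator assessment.

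**Conclusion.** The inconsistency is real and confined to Grade 3. The narrative rules out continuing the infusion, and the table permits it under conditions. This rests on one assumption, that *severe* includes Grade 3, which Section 4.4.2 does not state but the protocol's usage in Sections 1.2, 2.3 and 4.4.3 supports.

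The number of events is small: one serious reaction of Grade 3 or higher among about 494 programme patients, with non-serious Grade 3 events unknown. A reader might see a threat to the trial's results, but the documents do not support that. Infusion-related reaction is excepted from the general DLT criterion for other non-haematologic toxicity of Grade 3 or higher (Section 5.3.7). C2 and C3 exclude no patient from analysis (SAP Table 6.2:1). No endpoint, sample size or error rate has been shown to depend on the point.

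It is an internal contradiction in a safety instruction, not a design choice open to debate. It merits correction because it bears on re-exposure after a serious type of reaction and because correction is cheap. The infusion-time points are secondary matters of wording.

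**What to change.** Main change, in Protocol Section 4.4.2:

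- Tie *severe* to a CTCAE grade.
- Reconcile the narrative with the Grade 3 row so that one instruction covers resumption of the infusion.
- State how Section 2.3's deference to usual care or local guidelines relates to that instruction.

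Which rule applies is for the sponsor's clinical team; this review takes no position. Once it is settled, the C2 guidance should say whether a resumed Grade 3 infusion is a deviation.

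Secondary wording, in the same edit:

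- Align the grade condition for a longer infusion between Sections 4.1.1 and 4.1.4.1 (Grade 2 or higher) and Section 4.4.2 (no condition, rate halved at Grade 1).
- State whether the three-hour maximum counts interruptions, and use the same definition for C3 in the SAP.

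The cost is protocol wording, with a matching clarification in the SAP deviation table. No data collection, analysis or sample size changes.
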